1 TITLE PAGE

STATISTICAL ANALYSIS PLAN

**Study Protocol
Number:** E7777-G000-302

**Study Protocol
Title:** A Clinical Study to Demonstrate Safety and Efficacy of E7777 in
Persistent or Recurrent Cutaneous T-Cell Lymphoma

Date: 25 February 2022

Version: Final Version 2.0

REVISION HISTORY**Revisions to Version 1.0****Date: 25 February 2022**

Change	Rational	Affected Sections
Objective for Quality of Life (QoL) analysis is updated.	Addition of Lead-in subjects treated at the same dose provides a more complete population to assess QoL at 9 µg/kg/day, therefore QoL is expanded to include Lead-In subjects.	4.1.3 Exploratory Objective(s)
Full Analysis Set (FAS) and Safety Analysis Set are updated.	Addition of Lead-in subjects treated at the same dose provides a more complete population to assess safety at 9 µg/kg/day, therefore Safety Analysis Set is expanded to include Lead-In subjects. For completeness, the same additional subjects are included in FAS as well. The FAS and Safety Analysis Set now include all subjects in the Primary Efficacy Population.	6.2.1 Analysis Sets 8.1 Changes in the Planned Analyses from those in the Protocol
Analysis Set for Immunogenicity is updated.	To include all available data points for Immunogenicity analysis per protocol (Safety Analysis Set).	6.2.1, Table 1
Pharmacokinetic (PK) Analysis Set is updated.	The PK Analysis Set is expanded to include Lead-In subjects as well, so that all subjects treated at the 9 µg/kg/day dose can be pooled for analysis.	6.2.1 Analysis Sets 6.6.1 Pharmacokinetic Analyses
Best Overall Response (BOR) derivation rules for Global Response Score (GRS) per Olsen criteria are updated.	Additional details for derivation of BOR rule are inserted to provide clarification about additional scenarios of timepoint GRS responses. Clarification is also provided for: (1) rules on time interval needed for confirmation of response; (2) definition of date of response; (3) rules for handling missing/UNK GRS timepoint responses; and 4) rules for 2 progressive diseases (PDs) within 7 days being counted as a single PD event (which is based on a reasonable clinical picture of duration of disease flare and of how fast progression may occur).	6.4.1 Best Overall Response (BOR) based on GRS
“How to handle PD” for Prince criteria is added.	Clarification. Same rationale as that for BOR GRS per Olsen criteria	6.4.3 Best Overall Response (BOR)

		using Prince (2010)
Definition of Clinical Benefit Rate is updated.	Clinical Benefit Rate is based on CR, PR, or Durable SD (≥ 23 weeks).	6.5.3.1 Exploratory Efficacy Analyses 8.1 Changes in the Planned Analyses from those in the Protocol
Remove “pre” from wording “premedication in sensitivity analysis.	Typo in protocol, should be “steroid medication” instead of “steroid premedication”.	6.5.3.1 Exploratory Efficacy Analyses
Two figures are removed. Figure “Semi-log box plot for Anti-E7777 and Anti-IL-2 titers by cycle” is added.	To clarify ADA data types by assays rather than confirmation rate; Semi-log box plot will be used to present titer data rather than semi-log plot of titers from individual.	6.6.2 Immunogenicity Analysis
Dose intensity is removed. Definition for received dose as percentage of planned starting dose are updated.	Relative dose intensity as a percentage of actual total dose over total planned dose is more meaningful than dose intensity (as average daily dose) since the drug is given 5 days per 21-day cycle.	6.7.1 Extent of Exposure
The version of CTCAE grade is added.	To clarify that CTCAE version was upgraded from 4.03 to 5.0 in Protocol Amendment 05 (03 May 2018).	6.7.2 Adverse Events
QTc Bazett is removed.	QTc Bazett was not included in Protocol.	6.7.5 Electrocardiograms

3 LIST OF ABBREVIATIONS AND DEFINITIONS OF TERMS

Abbreviation	Term
AE	adverse event
AUC(0-t)	area under the curve from time 0 to time t
AUC(0-inf)	area under the curve from time 0 to infinity
ADaM	Analysis Data Model
BP	blood pressure
BSA	body surface area
BOR	Best Overall Response
CBR	Clinical Benefit Rate
CRF	case report form
CI	confidence interval
C _{max}	maximum concentration
COVID-19	coronavirus disease 2019
CR	complete response
CCR	clinical complete response
CTCAE	common terminology criteria for adverse events
CTCL	cutaneous T-cell lymphoma
CV	coefficient of variation
DOR	Duration of Response
ECG	Electrocardiogram
ECOG	Eastern Cooperative Oncology Group
eCRF	electronic case report form
EORTC	European Organization for Research and Treatment of Cancer
FACT-G	Functional Assessment of Cancer Therapy - General
FAS	Full Analysis Set
FDA	US Food and Drug Administration
GRS	Global Response Score
ICF	informed consent form
IRC	Independent Review Committee
IL-2	Interleukin-2

Abbreviation	Term
ISCL	International Society for Cutaneous Lymphomas
KM	Kaplan-Meier
MedDRA	Medical Dictionary for Regulatory Activities
mSWAT	modified Severity Weighted Assessment Tool
NE	not evaluable
ORR	Objective Response Rate
PFS	progression-free survival
PK	pharmacokinetic
PR	Partial Response
PD	Progression disease
PT	preferred term
Q1	first quartile
Q3	third quartile
QoL	Quality of Life
SAE	serious adverse event
SAP	statistical analysis plan
SD	stable disease
SE	standard error
SI	Système International
SOC	system organ class
TEAE	treatment-emergent adverse event
TLG	tables, listings, and graphs
$t_{1/2}$	Elimination half-life
t_{max}	Time to maximum concentration
TTP	Time to Progression
TTR	Time to Response
TNMB	tumor-node-metastasis-blood
UNK	unknown
VAS	visual analog scale
Vd_{ss}	Volume of distribution at steady state

Abbreviation	Term
WHO	World Health Organization

4 INTRODUCTION

Protocol E7777-G000-302 consists of an initial Lead-In part followed by the Main Study. The Lead-In part was conducted between May 2013 and August 2015 and a clinical study report (CSR) for lead-in part was completed in January 2019.

This statistical analysis plan (SAP) is to describe the procedures and the statistical methods that will be used to analyze and report results for the Main Study. The primary efficacy population will include a subset of subjects from the Lead-in part as described in Protocol Amendment 06.

4.1 Study Objectives

The efficacy analyses will be performed primarily in the Stage I – III subjects from Main Study (approximately 65) plus the Stage I – III subjects from the 9 µg/kg/day dose group in Lead-In Study (approximately 5), and additional analyses will be performed in all subjects (both Main Study and Lead-In) who received study drug at 9 µg/kg/day dose.

4.1.1 Primary Objective(s)

To demonstrate efficacy of E7777 in subjects with recurrent or persistent cutaneous T-cell lymphoma (CTCL) in Stage I – III subjects as assessed by objective response rate (ORR); Objective response is complete response [CR] and partial response [PR], according to International Society for Cutaneous Lymphomas (ISCL)/ European Organization for Research and Treatment of Cancer (EORTC) Global Response Score (GRS) [Olsen 2011])¹.

4.1.2 Secondary Objective(s)

- To determine the duration of response (DOR) for E7777
- To determine time to response (TTR) after E7777 treatment
- To determine skin response after E7777 treatment
- To determine duration of skin response after E7777 treatment
- To determine time to skin response after E7777 treatment
- To assess ORR for E7777 using the alternate response assessment criteria of Prince (2010)²
- To evaluate safety and tolerability of E7777 in all subjects
- To evaluate safety and tolerability of E7777 in the Stage I – III Main Study subjects plus the Stage I – III Lead-In subjects from the 9 µg/kg/day dose group
- To characterize the pharmacokinetics (PK) of E7777 and immunogenicity after treatment with E7777

4.1.3 Exploratory Objective(s)

- To assess the following efficacy endpoints for subjects treated with E7777: progression-free survival (PFS) and time to progression (TTP) (using GRS)
- To assess pruritus improvement reported by subjects treated with E7777

- To assess Quality of Life (QoL) for (1) all subjects (both Main Study and Lead-In) who received study drug at 9 µg/kg/day dose, (2) Stage I – III subjects from Main Study plus Stage I – III subjects from the 9 µg/kg/day dose group in Lead-In Study.

4.2 Overall Study Design and Plan

This is a multicenter open-label, single-arm study of E7777 in subjects with recurrent or persistent CTCL.

A sufficient number of subjects in the Main Study will be recruited so that approximately 70 Stage I – III subjects from both the Main Study and the Lead-In Study in the 9 µg/kg/day dose group with recurrent or persistent CTCL are treated with E7777 to assess efficacy. Safety will be evaluated in all subjects from the Main Study, and in Lead-In subjects from the 9µg/kg/day dose group. The dose of E7777 in the Main Study is selected from results of the Lead-In part of the study. The primary efficacy analysis will be based on Stage I – III subjects treated at 9 µg/kg/day, which includes subjects from both the Main Study plus the Lead-In.

Study Phases for Each Subject

Subjects in the study will move through three phases while on study.

- **Pretreatment Phase** includes a Screening Period and a Baseline Period:
 - **Screening Period** is from Day -28 to the start of treatment (Cycle 1 Day 1) except for signing of the informed consent form (ICF) which may have been up to 8 weeks before the first dose of study drug. The purpose of the Screening Period is to obtain informed consent and to ensure that each subject met all the specified eligibility criteria.
 - **Baseline Period** is from Day -7 to the start of treatment. Subjects who completed the Baseline assessments and met the eligibility criteria began treatment in the Treatment Phase.
- **Treatment Phase** consists of the following periods:
 - **Treatment Period.** E7777 will be administered by intravenous (IV) infusion over 60 minutes (± 10 minutes) on 5 consecutive days every cycle of 21 days. Treatment with E7777 for up to 8 cycles; each cycle of 21 days is one Period. Subjects who attained skin tumor response and derived clinical benefit from E7777 treatment could continue receiving treatment beyond 8 cycles, at the discretion of the treating physician.
 - **Follow-Up Period.** Tumor assessment until discontinuation of treatment due to progressive disease (PD); immunogenicity, and survival follow-up until relapse or initiation of new systemic anti-cancer therapy. All Follow-up assessments will be performed for up to 3 years after end of treatment, or until sponsor termination of the study.

After data cutoff for the primary analysis in the Main Study, the study moved to the Extension Phase.

- **Extension Phase** consists of the following periods:

- **Treatment Period**, for continued treatment of subjects with ongoing treatment at data cutoff. Subjects will be treated for up to 8 cycles. Subjects with attained skin tumor response and deriving clinical benefit from E7777 treatment may continue receiving treatment beyond 8 cycles, at the discretion of the treating physicians.
- **Follow-Up Period**. Tumor assessment until discontinuation of treatment due to PD; immunogenicity, and survival follow-up until relapse, or initiation of new systemic anticancer therapy. All Follow-up assessments will be performed for up to 3 years after the end of treatment, or until sponsor termination of the study.

Pharmacokinetics and Immunogenicity

In the Lead-in, initial serial PK sampling at dose levels 6 to 15 µg/kg had been performed. Immunogenicity had also been assessed at these dose levels. In the Main Study, limited serial and sparse PK samples will be used to characterize PK, and the relationship of 9 µg/kg/day exposure and primary efficacy.

PK assessment of E7777 will be based on the first 12 subjects in the Main Study, using serial blood PK sampling on Day 1 in Cycles 1, 3, and 5, with sparse sampling in Cycle 8. In addition, sparse sampling obtained in the Main Study on the rest of the subjects on Day 1 of Cycle 1 will be assessed.

Immunogenicity (formation of antibodies to E7777 or Interleukin-2 (IL-2), and of neutralizing antibodies) will be assessed in all subjects in the Main Study. A predose blood sample for immunogenicity assessment will be collected before Day 1 dosing in Cycles 1, 2, 3, 5, and 8; after that, subjects tested positive at any time for anti-IL-2 will be followed up for immunogenicity testing for anti-IL-2 on a 6-month schedule for one year and every year thereafter until antibody titers decrease to baseline level or upon study termination.

Please see Table 4 of the Protocol (Schedule of Assessments) for more details on study procedures.

Timing of Primary Analysis for the Main Study

The primary analysis will be performed after data cutoff, which will be either of the following two events, whichever occurs later: (1) when all subjects in the Main Study have either completed Cycle 8 or are off treatment, or (2) when all subjects with at least one documented time point response of PR or better have undergone the subsequent tumor assessments necessary for confirmation of response (unless the subject had disease progression or discontinued from study before that).

5 DETERMINATION OF SAMPLE SIZE

The sample size of approximately 70 Stage I - III subjects (including Stage I - III subjects from both the Main Study and the Lead-In part 9µg/kg/day dose group combined) was estimated assuming that the lower bound of the 2-sided 95% Confidence Interval (CI) of ORR exceeding 25% which indicates clinical benefit in persistent and recurrent CTCL. With a sample size of 70, the 2-sided 95% exact Clopper-Pearson confidence interval of an

observed 36% ORR (i.e., 25 subjects with CR+PR among 70 subjects) would be with lower bound of 25% and upper bound of 48%.

Sample size estimates were calculated using PASS 2008 software.

6 STATISTICAL METHODS

All descriptive statistics for continuous variables will be reported using mean, standard deviation (SD), median, first quartile (Q1), third quartile (Q3), minimum and maximum. Categorical variables will be summarized as number (percentage) of subjects.

6.1 Study Endpoints

Tumor responses (based on the Olsen criteria) assessed by an Independent Review Committee (IRC) will be used in the evaluation of primary efficacy endpoint, and the associated secondary and exploratory efficacy endpoints. In addition, the IRC will assess tumor responses using Prince criteria, which is a separate secondary endpoint. Investigator-assessed tumor response (based on the Olsen criteria) and the associated secondary and exploratory response endpoints will also be reported.

6.1.1 Primary Endpoint(s)

The primary efficacy endpoint is ORR assessed by IRC based on Global Response Score (GRS) (Olsen 2011)¹.

6.1.2 Secondary Endpoint(s)

- DOR based on GRS
- TTR based on GRS
- ORR assessed by investigator using GRS (Olsen 2011)¹
- Objective response assessed by IRC using Prince (2010)²
- Skin response (according to modified Severity Weighted Assessment Tool (mSWAT))
- Duration of skin response
- Time to skin response
- Safety parameters
- PK parameters
- Immunogenicity

6.1.3 Exploratory Endpoint(s)

- PFS and TTP
- Clinical Benefit Rate (CBR)
- Pruritus improvement
- QoL using Skindex-29 and the FACT-G Questionnaire

6.2 Study Subjects

6.2.1 Analysis Sets

The definitions of the analysis sets are provided below:

All Enrolled Subjects: All subjects in Main Study who signed informed consent, and at Screening were assessed as meeting all inclusion criteria and not meeting any exclusion criteria.

Full Analysis Set: All subjects (both Main Study and Lead-In) who received study drug at 9 µg/kg/day dose.

Primary Efficacy Analysis Set: All Stage I – III subjects (both Main Study and Lead-In) who received study drug at 9µg/kg/day dose.

Safety Analysis Set: All subjects dose (both Main Study and Lead-In) who received study drug at 9 µg/kg/day. This will be the analysis set for all safety analyses.

Stage I-III Safety Analysis Set: All Stage I – III subjects (both Main Study and Lead-In) who received study drug at 9µg/kg/day dose.

Per Protocol Set: All subjects had a baseline and at least one post-dose tumor assessment and had no major protocol deviations in either Primary Efficacy Analysis Set or Full Analysis Set. The per protocol analysis set will be the secondary analysis set for efficacy endpoints.

PK Analysis Set: All subjects from whom at least one quantifiable concentration of E7777 was observed at 9 µg/kg/day dose (both Main Study and Lead-In) will comprise the analysis set for the PK data.

Population PK Analysis Set: All subjects from whom at least one quantifiable concentration of E7777 is available with a documented dosing history from both Lead-in and Main Study.

Population PK/PD Analysis Set: All subjects in the Population PK analysis set for whom efficacy and safety variables are also available from both Lead-in and Main Study.

The number (percentage) of subjects included in each analysis set will be presented.

Table 1 summarizes which analyses each analysis set will be primarily used for.

	Full	Primary Efficacy	Safety	Stage I-III Safety	Per Protocol	PK Analysis Set
Disposition	•	•				
Demography & Baseline Characteristics	•	•				
Disease History	•	•				
Prior & Concomitant Medications	•	•				
Tumor Response per Olsen criteria by Investigator assessment	•	•				
Tumor Response per Olsen criteria by IRC review	•	•			•	
Tumor Response per Prince criteria by IRC review		•				
Skin Response	•	•				
Progression-Free Survival	•	•				
Time to Progression	•	•				
Patient Pruritus	•	•				
Drug Exposure			•	•		
Adverse Events			•	•		
Laboratory Tests			•	•		
Vital Signs			•	•		
ECGs			•	•		
Pharmacokinetic serum/parameter						•
Immunogenicity			•			

6.2.2 Subject Disposition

Enrolled subjects include all subjects who signed informed consent forms in the Main Study. The number of subjects screened, the number (percentage) of subjects who failed screening and the reasons for screen failure, will be summarized based on data reported on the Screening Disposition CRF.

The disposition status of subjects for both the Primary Efficacy Analysis Set and Full Analysis Set will be summarized based on data reported on the Study Disposition Treatment Phase CRF. Also, subjects discontinued from treatment but on survival follow-up at the data cutoff date will be summarized. In addition, subjects discontinued study and the reasons for discontinuation will also be summarized.

A distribution of the number of subjects by each country and site will be provided.

6.2.3 Protocol Deviations

All protocol deviations will be identified by reviewing the data prior to database lock for primary analysis. Major protocol deviations will be appropriately summarized by site and grouped into different categories. All major protocol deviations identified according to study entry criteria and during treatment will be listed. All protocol deviations related to COVID-19 will be listed.

6.2.4 Demographic and Other Baseline Characteristics

Demographic and Baseline characteristics will be presented using summary statistics and listings for both the Primary Efficacy Analysis Set and Full Analysis Set.

6.2.4.1 Demography

Continuous demographic and Baseline variables include:

- Age (year)
- Height (cm)
- Weight (kg)
- Body Surface Area (BSA)(m²): $BSA = \text{SQRT}([\text{Height}(\text{cm}) \times \text{Weight}(\text{kg})] / 3600)$

Categorical variables include:

- Sex (male/female)
- Age group (year): <65 years, ≥65
- Ethnicity: Hispanic or Latino, Not Hispanic or Latino
- Country: Australia and United States
- Race
 - White
 - Black or African American
 - Asian
 - Japanese
 - Other Asian
 - American Indian or Alaska Native
 - Native Hawaiian or other Pacific Islander
 - Other
- Race group: White, Asian and all others
- ECOG performance status (0 to 2)

6.2.4.2 Disease characteristics

Disease history and characteristics at study entry including type of CTCL (Mycosis Fungoides (MF)/Sezary Syndrome (SS)), CTCL disease stage at baseline, CTCL disease staging, tumor-

node-metastasis-blood (TNMB) stage at study entry, mSWAT (modified Severity Weighted Assessment Tool) score at baseline and pruritus VAS at baseline will be summarized.

6.2.5 Medical history

A subject data listing of medical and surgical history will be provided. Medical history will be coded using Medical Dictionary for Regulatory Activities (MedDRA) (version 24.0 or most recent version).

6.2.6 Prior Anticancer Therapy

Prior anticancer therapies tables will be presented for both Primary Efficacy Analysis Set and Full Analysis Set, also listings will be provided.

Number of subjects with prior anti-cancer therapies, number of therapies (including medication and non-medication) and duration of last therapy, and best response to the last therapy, and non-medication therapy category will be summarized for prior anticancer therapies. Prior anti-cancer medications and non-medication therapies will be summarized separately.

6.2.7 Prior and Concomitant Medications

Prior and concomitant medications tables will be presented for both Primary Efficacy Analysis Set and Full Analysis Set, also listings will be provided.

All investigator terms for medications recorded in the CRF will be coded to an 11-digit code using the World Health Organization Drug Dictionary (WHO DD) version of March 2021 or most recent version. The number (percentage) of subjects who took prior and concomitant medications will be summarized by Anatomical Therapeutic Chemical (ATC) Classification and WHO drug preferred term. Prior medications include medications that started prior to first dose of study drug. Concomitant medications are defined as medications that (1) started before the first dose of study drug and were continuing at the time of the first dose of study drug, or (2) started on or after the date of the first dose of study drug but within 30 days after the end date of exposure of study drug.

Premedication for E7777 is required in cycles 1 to 3 and is optional from cycle 4 onward. Premedications will be listed based on an indication of "Premedication" on prior and concomitant CRF. Steroid premedications during study will also be summarized by number (percentage) of subjects who took steroid premedication in total and during each cycle.

6.3 Data Analysis General Considerations

6.3.1 Pooling of Centers

Subject data from all centers will be pooled for all analyses. Center will not be considered as a factor in the analyses.

6.3.2 Adjustments for Covariates

No adjustment for covariates will be made for this study.

6.3.3 Multiple Comparisons/Multiplicity

Not applicable.

6.3.4 Examination of Subgroups

Baseline disease stage subgroup analysis for efficacy endpoints ORR, DOR, TTR, CBR, skin response, duration of skin response and time to skin response may be provided as appropriate.

For Primary Analysis Set, disease stage subgroup categories may include IA/IB/IIA; IIB; and IIIA/IIIB as appropriate; for Full Analysis Set, disease stage grouping categories may include IA/IB/IIA; IIB; IIIA/IIIB; and IVA/IVA1/IVA2 as appropriate.

Additional subgroup analyses may also be conducted, if deemed appropriate.

6.3.5 Handling of Missing Data, Dropouts, and Outliers

Adverse Events with incomplete start dates will be considered treatment emergent if:

- a) Day and month are missing and the year is equal to or after the year of the first dose date;
- b) Day is missing, and the year is after the year of the first dose;
- c) Day is missing and the year is equal to the year of the first dose date and the month is equal to or after the month of the first dose date;
- d) Year is missing; or
- e) Complete date is missing.

Medications will be considered concomitant if:

- a) Day and month are missing and the year is equal to or after the year of the first dose date;
- b) Day is missing, and the year is after the year of the first dose;
- c) Day is missing and the year is equal to the year of the first dose date and the month is equal to or after the month of the first dose date; or
- d) Year is missing; or
- e) Complete date is missing.

For incomplete dates involving efficacy and other safety data, a conservative imputation will be used for calculation if needed. More details of imputation rules will be specified in study analysis dataset specification.

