### 9.5.7 Reporting of SAEs, Pregnancy, and Other Events of Interest

#### 9.5.7.1 Reporting of SAEs

**All SAEs, regardless of their relationship to study treatment, must be reported on a completed SAE form by email or fax as soon as possible but no later than 1 business day from the date the investigator becomes aware of the event.**

**Deaths and life-threatening events should be reported immediately by telephone. The immediate report should be followed up within 1 business day by emailing or faxing the completed SAE form.**

SAEs, regardless of causality assessment, must be collected through the last visit and for 30 days after the subject's last dose. All SAEs must be followed to resolution or, if resolution is unlikely, to stabilization. Any SAE judged by the investigator to be related to the study treatment should be reported to the sponsor regardless of the length of time that has passed since study completion.

The detailed contact information for reporting of SAEs is provided in the Investigator Study File.

**For urgent safety issues**, please ensure all appropriate medical care is administered to the subject and contact the appropriate study team member listed in the Investigator Study File.

It is very important that the SAE report form be filled out as completely as possible at the time of the initial report. This includes the investigator's assessment of causality.

Any follow-up information received on SAEs should be forwarded within 1 business day of its receipt. If the follow-up information changes the investigator's assessment of causality, this should also be noted on the follow-up SAE form.

Preliminary SAE reports should be followed as soon as possible by detailed descriptions including copies of hospital case reports, autopsy reports, and other documents requested by the sponsor.

The investigator must notify his/her IRB/IEC of the occurrence of the SAE, in writing, if required by the institution. A copy of this communication must be forwarded to the sponsor to be filed in the sponsor's Trial Master File.

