Durable Stable disease must be achieved at ≥ 23 weeks after first dose of study drug to be considered best overall response based on Olsen (2011)¹ criteria.

The 2-sided, exact 95% CI of CBR will be calculated using the Clopper-Pearson method.

PRURITUS IMPROVEMENT

Subjects will rate the severity of pruritus using a 100-mm visual analog scale (VAS), on which zero indicates no itch and 100 indicates worst possible itch. A clinically significant improvement is defined as an absolute decrease of 20 mm from baseline maintained for ≥ 4 weeks; baseline score must be ≥ 20 . Subject's pruritus improvement rate is defined as the proportion of subjects with a clinically significant improvement in pruritus. The 2-sided, exact 95% CI of pruritus improvement rate will be calculated using the Clopper-Pearson method.

In addition, the percentages of subjects who have $\geq 20\%$ and $\geq 50\%$ improvements (decreases) relative to baseline will be tabulated.

SENSITIVITY ANALYSES

Sensitivity analyses for ORR in subjects receiving versus subjects not receiving steroid medication for any cycle during the study will be performed. ORR (the proportion of

subjects achieving a BOR of confirmed CR or PR) will be summarized along with the 2-sided, exact 95% CI, using the Clopper-Pearson method.

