6.7.2 Adverse Events

Adverse events will be summarized for the Safety Analysis Set and Stage I-III Safety Analysis Set. Adverse events were graded using Common Terminology Criteria for Adverse Events (CTCAE) version 4.03 or version 5.0. CTCAE version was upgraded from 4.03 to 5.0 in Protocol Amendment 05 (03 May 2018). Investigators will collect all AE CTCAE grades (for both increasing and decreasing severity). AEs will be classified into standardized

medical terminology from the verbatim description using the Medical Dictionary for Regulatory Activities (MedDRA version 24.0 or most recent version). AEs will be summarized by preferred term (PT) nested within system organ class (SOC). All AEs will be listed.

A TEAE is defined as an AE that emerged during treatment or up to 30 days (also 30 days for serious TEAEs) following last dose of study drug; AEs that emerge during study drug treatment, having been absent at pretreatment (Baseline), or those that:

- Reemerge during study drug treatment, having been present at Baseline but stopped prior to study drug treatment, or
- Worsen in severity during study drug treatment relative to the pretreatment state, when the AE is continuous.

Only those AEs that are treatment emergent will be included in summary tables. All AEs, treatment emergent or otherwise, will be presented in subject data listings.

An overview table, including the incidence of and the number of subjects with treatment-emergent adverse events (TEAEs), SAEs, deaths, and those TEAEs that led to discontinuation from study drug, dose reduction or drug interruption, will be provided. The incidence of TEAEs will be summarized by SOC, PT, CTCAE grade, and relatedness to study drug (possibly related or probably related). Although a MedDRA term may be reported more than once for a subject, that subject will be counted only one time in the incidence count for that MedDRA term with the highest CTCAE grade (in the summary by CTCAE grade) or with the closest relationship to study treatment (in the summary by relatedness to study treatment). Treatment-related TEAEs includes TEAEs considered by the Investigator to be possibly or probably related to study drug or TEAEs with missing causality.

Separate summary tables and listings will be provided for all TEAEs, treatment-emergent SAEs, TEAEs reported as treatment-related, treatment-emergent SAEs reported as treatment-related, TEAEs by CTCAE grade, and TEAEs leading to treatment discontinuation.

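### The SAP's incomplete-date rules test only against the first dose, so some adverse events and medications known to lie outside the analysis window are still counted as treatment-emergent or concomitant

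*SAP*

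**What the plan says.** SAP 6.3.5 introduces the event rule with "Adverse Events with incomplete start dates will be considered treatment emergent if" and lists five conditions:

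- a) day and month missing, year equal to or later than the first-dose year;
- b) "Day is missing, and the year is after the year of the first dose";
- c) same year as the first dose, month no earlier than the first-dose month, day unknown;
- d) year missing;
- e) "Complete date is missing".

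The medication rule repeats the five conditions but does not say whether the incomplete date is the start or the stop.

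The definitions that these rules serve need more than the first-dose date. SAP 6.7.2 defines a treatment-emergent event as "an AE that emerged during treatment or up to 30 days (also 30 days for serious TEAEs) following last dose of study drug", with further clauses for events that re-emerge or worsen on treatment. SAP 6.2.7 calls a medication concomitant in two cases: (1) it began before the first dose and was still being taken at that dose, or (2) it began "on or after the date of the first dose of study drug but within 30 days after the end date of exposure".

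On collection, Protocol 9.5.4.1 starts adverse event recording at consent, and Protocol 9.1.4 allows consent up to 8 weeks before the first dose. Protocol 9.5.7.1 says "SAEs, regardless of causality assessment, must be collected through the last visit", and adds a 30-day period counted from the last dose. It sets no time limit for serious events that the investigator judges related to treatment.

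**The concern.** A worst-case rule for partial dates is normal and sensible when the date could fall on either side of a boundary. These rules go further. They also count records where the known data settle the matter the other way, because the two items that would settle it (the stop date and the last dose plus 30 days) are never consulted. The SAP then gives two answers for the same record: counted under 6.3.5, not counted under 6.7.2 or 6.2.7. A programmer must choose one, and the safety and concomitant-medication tables depend on that choice. In a registrational study with about 70 Stage I-III subjects, the classification rule should agree with the definition.

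**Working it through.** No sample size, power or stated figure depends on this point, so there is no plan figure to reproduce. The check applies the five conditions literally to constructed records and compares each result with the definitions.

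**Assumed dates (illustrative).** First dose 18 Nov 2019; eight undelayed 21-day cycles with five daily doses each (SAP 4.2).

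- Last dose: 7 × 21 + 4 = 151 days after first dose = 17 Apr 2020.
- End of window: last dose + 30 days = 17 May 2020.
- Earliest consent: 8 weeks (56 days) before first dose = 23 Sep 2019.

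| # | Record | Condition met | 6.3.5 result | What the known data show |
|---|---|---|---|---|
| 1 | Event, start Nov 2019 (day unknown), stopped 10 Nov 2019 | c | counted | ended before first dose |
| 2 | Event, start 2019 (day and month unknown), stopped 5 Nov 2019 | a | counted | ended before first dose |
| 3 | Medication, start year unknown, stopped 1 Mar 2015 | d | counted, if the rule refers to start dates | ended years before first dose |
| 4 | Event, start Mar 2021 (day unknown) | b | counted | earliest start 1 Mar 2021, 288 days after the window |
| 5 | Event, start 2022 (day and month unknown) | a | counted | earliest start 1 Jan 2022, after the window |
| 6 | Event, start Feb 2020 (day unknown) | b | counted | within treatment; rightly counted |
| 7 | Medication, start Jun 2019 (day unknown), ongoing | none | not reached by the rule | concomitant under 6.2.7 definition (1) |

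Records 1 to 5 contradict the SAP's own definitions. Record 6 shows the rule doing its proper work. Record 7 is not an error, because 6.2.7 decides it directly.

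**How such records can arise.** Records 1 and 2 need an event in the span of up to 8 weeks between consent and first dose, when recording is already active. Record 3 needs an earlier medication with an unknown start year; Protocol 9.3.1 requires every subject to have had prior therapy. Records 4 and 5 need an entry made after routine collection has ended, in practice a late-reported related serious event.

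**Scale of one misclassification.** Stage I-III set of about 70: 1/70 = 1.4 points. Full safety set: its size is not stated. The protocol plans about 115 subjects in total and about 20 in the Lead-In, so about 95 in the Main Study, plus the Lead-In subjects at 9 µg/kg/day. For sizes from 95 to 115, one subject is 1/95 = 1.1 to 1/115 = 0.9 points. SAP 6.7.2 counts a subject once per term, so a rate moves only if that subject does not already have the term.

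**Effect of adding the two missing checks.** If a record is not counted when a known stop precedes the first dose, or when its earliest possible start is after last dose + 30 days, records 1 to 5 drop out and record 6 stays in.

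**The case against.** Four arguments on the other side deserve weight.

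1. *Over-counting is a conservative convention for safety.* The direction is indeed conservative for adverse events. But a worst-case convention resolves uncertainty, and in records 1 to 5 none is left to resolve.

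2. *Collection stops at 30 days anyway.* Footnotes d and n of the Schedule of Assessments (Protocol Table 4) end medication review and adverse event assessment 30 days after the last dose, and Protocol 9.5.4.1 gives the same period for serious events. This largely stands. It reduces the upper-limit gap to late related serious events and anything entered under the looser last-visit wording. Serious events are also reported within one business day of awareness, so an unknown onset day should be uncommon. The stop-date gap is untouched by these limits.

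3. *The programming specifications may contain the checks.* They may; they are not among the documents. SAP 6.3.5, however, states the event and medication rules outright and sends only efficacy and other safety dates to the dataset specification. The general pointer in SAP section 9 states no override.

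4. *The medication rule may refer to stop dates.* If so, record 3 is not caught. That stands as an ambiguity, and the medication part of this point is conditional on the start-date reading.

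A reader might also infer three stronger consequences that the documents do not support:

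- *Ongoing medications with a partial start before the first dose are lost.* The conditions are sufficient, not exclusive, and definition (1) of 6.2.7 already makes such medications concomitant.
- *New therapies begun in follow-up appear as concomitant.* Scheduled medication review has ended by then, and nothing shows that such therapies enter that dataset.
- *The steroid response comparison is distorted.* SAP 6.5.3.1 plans "Sensitivity analyses for ORR in subjects receiving versus subjects not receiving steroid" medication for any cycle during the study; it does not say that the grouping uses the concomitant flag.

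**Conclusion.** The point holds as an internal contradiction in the SAP with a probably small effect. SAP 6.3.5 forces into the treatment-emergent count events whose recorded data place them outside the window in 6.7.2. If its medication rule refers to start dates, it does the same to medications against 6.2.7. The likelier route is a record that had stopped before the first dose; the late-event route is rarer.

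The error can only inflate counts. Each affected subject moves a rate by at most 1.4 points in the Stage I-III set and by about 1 point in the full safety set, whose size is assumed. The total cannot be estimated, because the frequency of partial dates is not given. The primary response rate is unaffected. The conclusion rests on the SAP text as written, since the programming specifications could not be checked.

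**What to change.** In SAP 6.3.5:

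- State that the medication rule applies to incomplete start dates.
- Add one exception to both rules: the record is not counted if a known stop date is before the first dose, or if the earliest date consistent with the known part of the start date is after last dose + 30 days.
- Say that records which remain ambiguous stay counted, and that the worsening and re-emergence clauses of 6.7.2 and definition (1) of 6.2.7 continue to apply.

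Do not add a blanket exclusion for events whose known start is before the first dose. It would drop pre-existing events that worsen on treatment, which 6.7.2 counts.

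The cost is about two sentences in the SAP, a matching line in the programming specification and a small programming change using start and stop dates. No new data collection is needed.
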